5.4.1.2. Compliance with study treatment

Data on capsules/tablets dispensed/returned are not collected on the CRF, and so compliance cannot be assessed in this way. As a proxy, compliance is assessed as a percentage, calculated as:

(Cumulative exposure over defined exposure period with interruptions excluded / Cumulative exposure over defined exposure period with interruptions included) *100.

Corresponding categorical variables are derived for compliance in the categories: $< 80\%, \ge 80 - < 90\%, \ge 90 - < 95\%, \ge 95 - <= 100\%, =100\%$.

Compliance with study treatment is derived as:

- [duration of exposure with all interruptions excluded / duration of exposure with interruptions included (except interruption for planned pregnancy)] \times 100.

All other exposure and compliance variables will be defined in the same way, i.e., excluding the planned pregnancy interruption periods. In addition, the planned pregnancy interruptions will not be counted/considered an interruption for the variables: number of subjects with at least an interruption, number of treatment interruptions (> 3 days) or cumulative duration of interruptions.

5.4.1.3. Study treatment re-initiation

A subject is considered to have a re-initiation of study treatment if they have a record in the study drug log where:

- There is a record in EX indicating 'Up-titration', 'Re-initiation', or 'Transition' with an associated administered dose of ponesimod 10 mg;
- This record follows a period of > 3 days where study drug was interrupted (either within a treatment period, or between two treatment periods).

The number of re-initiations per subject in AP3 is counted.

For subjects initially on placebo who had a treatment interruption before starting ponesimod treatment, the re-start of treatment after the interruption will not be considered as a re-initiation.

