		• To introduce the 2-week gradual uptitration regimen, to be used in case of re-initiation of study drug during TP3.
		• To amend the guidance for re-initiation of study treatment in the event of study treatment interruption in order to allow patients without the identified cardiovascular risk factors to re-initiate study drug at home.
		• To provide guidance regarding conduct of the study during the COVID-19 (coronavirus) pandemic.
		• To introduce guidance for subject monitoring and discontinuation in case of liver enzyme abnormalities.
		• To align the cardiovascular criteria for discontinuation with that used in Phase 3 clinical studies with ponesimod.

Ponesimod / ACT-128800/ JNJ-67896153 Multiple Sclerosis		EudraCT 2009-011470-15 EDMS-ERI-206617631
Protocol AC-058B202	Confidential	
Version 12		
15 March 2022, page 19/179		

Amendment	Date	Main reason(s)
9 19Oct20		• To inform study sites that the Independent Data Monitoring Committee (IDMC) will be disbanded after the clinical database closure of the last ponesimod double-blind study, in line with the disbandment date agreed per the IDMC Charter.
		• To provide further guidance on study conduct if/when ponesimod becomes commercially available during the study and patients are switched from study drug to commercially available ponesimod.
		• To align the safety reporting procedures with Janssen Safety processes and standards following the integration of Actelion Safety into Janssen Safety.
		• To clarify procedures related to the reporting of multiple sclerosis (MS) relapses and align with the wording in the protocol for the ongoing Phase 3 study (AC-058B303/OPTIMUM-LT).
10	04May21	• To align instructions related to vaccination to those in the Investigator's Brochure.
		• To introduce the transition of paper Case Report Form (CRF) to electronic Case Report Form (eCRF).
		 To further clarify guidance regarding conduct of the study during the COVID-19 (coronavirus) pandemic and the deployment of COVID-19 vaccines. To update sponsor contact information.

EudraCT 2009-011470-15 EDMS-ERI-206617631

Ponesimod / ACT-128800/ JNJ-67896153 Multiple Sclerosis Protocol AC-058B202 Version 12 15 March 2022, page 20/179

Confidential

TITLE	Multicenter, randomized, double-blind, parallel-group extension to study AC-058B201 to investigate the long-term safety, tolerability, and efficacy of 10, 20, and 40 mg/day					

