3.6.2 Study drug interruption

Study drug interruption should be avoided.

If study drug intake is interrupted by the patient for any reason, she/he must immediately inform the primary investigator / treating neurologist.

Study drug may be temporarily interrupted in response to an AE, a diagnostic or therapeutic procedure, a laboratory abnormality, a planned pregnancy, or for administrative reasons. The permitted maximum duration of the study drug interruption is 81 weeks for planned pregnancies and 12 weeks for other reasons (if exceeded, the patient will then be prematurely discontinued from the study).

In the event of a re-initiation of study drug, one tablet of ponesimod 2, 3, 4, 5, 6, 7, 8, 9, or 10 mg will be taken orally o.d. during the uptitration period (Day 1 to 14). During the maintenance period, patients will continue to take one tablet of ponesimod 20 mg orally o.d. [Table 6]. If a blister kit with the starting dose of 2 mg is not available at the site, re-initiation should be delayed until it becomes available (temporary treatment interruption).

Detailed guidance on how to re-initiate study drug in the event of drug interruption is provided in Appendix 5.

EudraCT 2009-011470-15 EDMS-ERI-206617631

Ponesimod / ACT-128800 / JNJ-67896153 Multiple Sclerosis Protocol AC-058B202 Version 12 15 March 2022, page 68/179

Confidential

Treatment period	Duration	Dose regimen
Titration	Day 1 and 2	2 mg
Titration	Day 3 and 4	3 mg
Titration	Day 5 and 6	4 mg
Titration	Day 7	5 mg
Titration	Day 8	6 mg
Titration	Day 9	7 mg
Titration	Day 10	8 mg
Titration	Day 11	9 mg
Titration	Day 12 to 14*	10 mg
Maintenance	Day 15 until EOT3	20 mg

Table 6:2-week gradual uptitration regimen

* An additional visit 14 days (± 1 day) after the day of re initiation (Re initiation Day 15) is mandated for patients with cardiovascular risk factors [see Appendix 5], but may be scheduled for any patient at the discretion of the investigator / treating neurologist. The titration kit will therefore include 3 additional tablets (to be used if applicable) for treatment on Day 15 17 (i.e., dose regimen 20 mg).

EOT3 End of Treatment

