Appendix 5: Guidance for re-initiation of study drug in the event of drug interruption

If study drug intake (during uptitration or maintenance phase) is interrupted by the patient for any reason, she/he must immediately inform the primary investigator / treating neurologist.

Note that under no circumstances should a patient take more than one capsule per day during TP1 or more than one tablet per day during TP2 and TP3.

A schematic overview of the re-initiation algorithm is given in Figure 2.

Depending on the day, time, and duration of study drug interruption, the following procedures will be followed.

A) If the patient missed taking the dose in the morning:

- The dose should be taken at any time on the same day.
- Regular dosing should be resumed with the morning dose on the following day.

B) If the patient missed taking the dose for up to three consecutive days:

- Dosing should be resumed in the morning, with the same dose taken prior to study drug interruption.
- Study drug intake may be re-initiated by the patient at home.
- Patients must be instructed to contact the investigator immediately if they experience any symptoms of bradycardia (e.g., dizziness, vertigo, syncope).

C) If the patient missed taking the dose for four or more consecutive days, then the gradual uptitration scheme outlined in Table 6 (blister kit with starting dose of 2 mg) must be used:

1. Patients with cardiovascular risk factors (i.e., meeting any of the below-listed Criteria for Cardiac Monitoring at Site) will require cardiac monitoring and therefore must have their re-initiation of study drug performed at the site. On the day of the re-initiation of ponesimod, the patient must be monitored for at least 4 hours post-dose, following the cardiac assessment schedule and applying the discharge criteria as described in Appendix 2.

Criteria for Cardiac Monitoring at Site (cardiovascular risk factors):

- Sinus bradycardia HR <55 bpm;
- History or presence during the study of first or second degree Mobitz type I AV block;
- History or presence during the study of myocardial infarction or heart failure.

Ponesimod / ACT-128800 / JNJ-67896153 Multiple Sclerosis		EudraCT 2009-011470-15 EDMS-ERI-206617631
Protocol AC-058B202	Confidential	
Version 12		
15 March 2022, page 155/179		

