5.4.2.2. Study treatment re-initiation

The following variables for treatment re-initiation are summarized for AP3 on the PAS:

- Number of subjects with at least 1 re-initiation during the Analysis Period: frequency counts and percentages;
- Number of re- initiations per subject during the analysis period; descriptive statistics.

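### SAP 5.4.1.3 recognises a re-initiation only through a 10 mg record and was not updated for the 2 mg-start kit, so the retained re-initiation table may be too low (minor)

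*SAP*

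**What the plan says.** SAP 5.4.1.3 sets two conditions. There must be an EX record marked Up-titration, Re-initiation or Transition "with an associated administered dose of ponesimod 10 mg", and "This record follows a period of > 3 days where study drug was interrupted". SAP 5.4.2.2 keeps two summaries built on this rule for the Final CSR, over the whole ponesimod period (AP3): "Number of subjects with at least 1 re-initiation during the Analysis Period: frequency counts and percentages", and the number per subject. Unlike several neighbouring sections, it carries no note that the output is dropped.

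The protocol's amendment history gives this as a reason for Amendment 8 (14 May 2020): "To introduce the 2-week gradual uptitration regimen, to be used in case of re-initiation of study drug during TP3". Under Protocol 3.6.2, on a restart "one tablet of ponesimod 2, 3, 4, 5, 6, 7, 8, 9, or 10 mg will be taken orally o.d. during the uptitration period". Table 6 places the 10 mg step on Days 12 to 14. Appendix 5 C covers gaps of four or more days: "then the gradual uptitration scheme outlined in Table 6 (blister kit with starting dose of 2 mg) must be used". If the 2 mg-start kit "is not available at the site, re-initiation should be delayed until it becomes available"; no other starting dose is named.

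Footnote 20 of the schedule in SAP 6.13 refers to the gradual scheme, but the change tables in SAP 6.2 have no entry for 5.4.1.3.

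**The concern.** The dose condition fits a restart that begins at 10 mg. The kit begins at 2 mg, so its first record after the gap does not meet the condition, and a 10 mg dose appears only near the end. The SAP does not say whether the 10 mg record must come straight after the gap or may come at any later time. Neither document shows how a kit is entered in EX. Two programmers could therefore derive different counts from the same data.

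One descriptive safety table is at stake. It could show fewer re-initiations than took place in TP3. A related point concerns outputs removed from the Final CSR. SAP 5.4.4.3.2 and 5.4.5.3.1 drop the tables of adverse events and of heart-rate, PR and QTc outliers on Day 1 of a re-initiation because the interim report presented them. That interim predates the kit.

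**Working it through.** **Inputs.** The counting rule is from SAP 5.4.1.3, the kit from Protocol Table 6, and Amendment 8's date (14 May 2020) from the protocol's amendment history. The interim cut-off (31 March 2019) is from Protocol 1.3.2.3. The plan gives no figure to reproduce.

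**Gap condition.** More than 3 days in the SAP equals four or more whole days in Appendix 5 C, so the two agree. Only the dose condition differs.

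**Kit by day (mg).** 2, 2, 3, 3, 4, 4, 5, 6, 7, 8, 9, 10, 10, 10. That is 14 days, 11 of them below 10 mg (11/14 = 79%). The first 10 mg day is Day 12, which directly follows a 9 mg dose on Day 11. The 79% describes the regimen; it does not measure the error.

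**Rule applied to four cases.** The readings are assumptions, because the EX layout is not given:
- A: one line per kit, carrying the 2 mg starting dose.
- B: each step logged; the 10 mg record must come directly after the gap.
- C: each step logged and labelled; the 10 mg record may come at any later time.
- D: one line per kit, carrying the 10 mg top step.

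| Case | True | A | B | C | D |
|---|---|---|---|---|---|
| Restart at 10 mg | 1 | 1 | 1 | 1 | 1 |
| Kit completed | 1 | 0 | 0 | 1 | 1 |
| Kit stopped for good on Day 6 | 1 | 0 | 0 | 0 | 1 |
| Kit stopped on Day 6 for 4 or more days, then restarted and completed | 2 | 0 | 0 | 1 | 2 |

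Restarts at 10 mg are always counted. In these cases, any error for kit restarts is downward. Stopping during the kit is foreseen: Appendix 5 opens with "If study drug intake (during uptitration or maintenance phase) is interrupted by the patient for any reason".

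**Size.** If a share f of true restarts used the kit, readings A and B capture 1 − f of them. The documents do not give f. Over an assumed range, f = 0, 0.10, 0.25, 0.50 and 1 gives 100%, 90%, 75%, 50% and 0% captured.

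**Dating.** Under reading C a kit restart would be dated to Day 12 instead of Day 1. No output kept in the Final CSR uses that date.

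**Interim against kit.** From 31 March 2019 to 31 March 2020 is 366 days, and to 14 May 2020 another 44, so 410 days in total. The interim cannot contain restarts under the Amendment 8 regimen.

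**The case against.** The strongest reply is that the Final CSR already shows most of what this table might miss. SAP 5.4.1.1 measures each interruption from the last dose before it to the restart, so every counted interruption ends in a restart. SAP 5.4.2.1 reports interruptions over 3 days, and subjects with at least one, without a dose filter. Planned-pregnancy interruptions are left out there (5.4.1.2), but restarts after them have their own disposition rows (5.2.2). An undercount would thus be visible from other tables. This stands, and it is why the point is minor.

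A reader might infer that kit restarts are never counted, or that a kit stopped before Day 12 is missed however it is logged. The documents do not support either. Reading C counts a completed kit, and reading D counts all of them.

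A reader might also infer that restart safety data are lost. They are not: the overall treatment-emergent tables are retained, and the ECG abnormality tables use all assessments, pre- or post-dose (5.4.5.3.1). Only the separate restart-day view is absent.

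It is also fair to object that removing the dose condition outright would admit resumptions with no uptitration, particularly through the Transition label. The fix has to guard against this.

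**Conclusion.** The rule in SAP 5.4.1.3 does not match the restart regimen introduced by Amendment 8, and SAP 6.2 records no decision to leave it so. The table in 5.4.2.2 may be too low for TP3 restarts made with the kit, most clearly those stopped before Day 12. The size is unknown and may be zero, because neither the number of kit restarts nor the EX layout is given. All objectives are exploratory, and no efficacy or exposure output depends on the rule. It is a minor defect, worth correcting because correction is cheap.

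On the secondary point, prior presentation in the interim is not a valid reason for dropping the Day-1 re-initiation adverse event and ECG tables as far as kit restarts are concerned; another reason might be. Restart-day blood pressure is mixed: SAP 5.4.5.2.1 adds that it is no longer required, whereas the change table in 6.2.3 gives only the interim as the reason for removal.

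Separately, schedule footnote 12, in the protocol and copied into SAP 6.13, describes a single Day 8 step for TP3 restarts. This conflicts with Table 6 and Appendix 5 C, and the passages must be reconciled.

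**What to change.** In SAP 5.4.1.3:
- Define a re-initiation as the first record labelled Re-initiation, Up-titration or Transition after more than 3 days without study drug that begins an uptitration, whether under the 10 mg-start scheme or the Table 6 kit.
- Date it at the first dose after the gap and show counts by starting dose.
- List resumptions without uptitration separately.
- State how kit doses are held in EX.
- Log the change in SAP 6.2.

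Reconcile the result with interruptions over 3 days in 5.4.2.1, allowing for the exclusion of planned-pregnancy interruptions. Use the SV records of 5.2.1.5 only for restarts after planned pregnancy, the one purpose for which that rule is written.

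For the dropped Day-1 re-initiation adverse event and ECG tables, state a reason other than the interim. Align the blood-pressure reason in 6.2.3 with 5.4.5.2.1. Reconcile footnote 12 with Table 6 and Appendix 5 C.

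The cost is a few lines of SAP text and one derivation, with no new data collection. The replacement reason takes one sentence.

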5.4.2. Analysis of Exposure

5.4.2.1. Exposure and compliance

Separate exposure tables are created for the AP3 exposure period as defined in Table 10 in Section 5.4.1.1 and for the corresponding compliance variables defined in Section 5.4.1.2 to present:

- Ponesimod exposure (years): descriptive statistics;
- Overall subject years exposure (sum over all subjects' exposure);

```
CONFIDENTIAL – FOIA Exemptions Apply in U.S.
```

- Ponesimod exposure by category (cumulative) (years): frequency counts and percentages;
- Ponesimod exposure with interruptions excluded (years): descriptive statistics;
- Ponesimod exposure by category with **interruptions excluded** (cumulative) **(years):** frequency counts and percentages;
- Number of treatment interruptions > 3 days: frequency counts and percentages;
- Number of subjects with at least 1 treatment interruption > 3 days: frequency counts and percentages;
- Cumulative duration (days) of interruptions > 3 days: descriptive statistics;
- Compliance (%): descriptive statistics (AP3 only);
- Compliance by category (%): frequency counts and percentages (AP3 only).

Corresponding listings of all exposure and compliance variables as defined in Sections 5.4.1.1 and 5.4.1.2 are provided separately for each defined exposure period.

All outputs for ponesimod exposure are based on the PAS.

5.4.2.2. Study treatment re-initiation

The following variables for treatment re-initiation are summarized for AP3 on the PAS:

- Number of subjects with at least 1 re-initiation during the Analysis Period: frequency counts and percentages;
- Number of re- initiations per subject during the analysis period; descriptive statistics.

5.4.2.3. Study drug batches

A listing of study drug batches received by each subject, including lot numbers and date dispensed, will be created for AP3 on the PAS.

5.4.3. Adverse Events

An AE is any event reported by the investigator on the CRF. All adverse events are stored in the appropriate SDTM.AE domain.

AEs collected in the core study are stored in SDTM201.AE. New AEs collected in the extension study are stored in SDTM202.AE, together with follow-up of AEs that were ongoing at the end of the core study. The two AE datasets are concatenated for the purposes of this analysis, and the additional follow-up details collected for AEs that were ongoing at the time of the end of the core study are merged onto the original records to create a single record for each such AE.

All AEs reported in both SDTM201.AE and SDTM201.AE are coded to the MedDRA version 26.0.

Adverse events with a missing end date are considered as ongoing, i.e., the end date is set to missing.

5.4.3.1. Duration of AE (days) is derived as min [AE end date, EOS date] – AE start date + 1 day. Treatment-emergent adverse events

Treatment-emergent adverse events (TEAEs) are defined according to the general definition of treatment-emergent for safety variables as described in Section 5.1.4.

AEs with completely missing start date will be considered as treatment-emergent unless it is otherwise clear (e.g., by end date) that the event occurred pre-treatment. If it is not clear whether the event is treatment-emergent or not (in case of partial dates), the event will be considered a TEAE if the AE start date is potentially on or after treatment start date. For example, an AE with partial date of "May 2016" and a treatment start date of "23 May 2016" is considered treatment-emergent. For imputation of partial dates see definition in Section 6.14.4.

AEs with an onset date during treatment interruptions (including periods between studies and study-periods) except the period of planned pregnancy interruptions (see Section 5.1.4) are considered treatment-emergent.

AEs considered treatment-emergent are flagged in the AdaM dataset.

5.4.3.2. Post-treatment-emergent adverse events

Post-treatment-emergent adverse events are defined as those AEs occurring from 16 days after last administration of ponesimod until last study date, i.e., AEs occurring during the post-treatment-emergent period (Section 5.1.6)

5.4.3.3. Intensity of adverse events

The maximum intensity of an AE is stored in SDTM.AE.AESEV, as 'Mild', 'Moderate', 'Severe' or 'Not applicable'. Adverse events with missing intensity are considered in any analysis as 'Severe'.

5.4.3.4. Relationship of adverse events to treatment

The possible relationship of an AE to study treatment is stored in SDTM.AE.AEREL, as 'Related' or 'Not Related'. If the relationship is missing for an AE, then it is considered to be related.

5.4.3.5. Outcome of adverse events

The outcome of an AE is stored in SDTM.AE.AEOUT, as 'Recovered/resolved', 'Recovered/resolved with sequelae', 'Not recovered/not resolved', 'Fatal', or 'Unknown'.

5.4.3.6. Deaths

Death information (date of death and cause of death) is stored in SDTM.DD. Date of death is in DDDTC and cause of death is in DDSTRESC.

5.4.3.7. Serious adverse events

The seriousness of an adverse events is stored in SDTM.AE.AESER as 'Y' or 'N'. If missing, the AE is considered to be serious.

5.4.3.8. Adverse events leading to discontinuation of study treatment

The action taken for an adverse event is stored in SDTM.AE.AEACN. An AE is considered to be an AE leading to discontinuation if AEACN = 'Drug withdrawn'.

5.4.3.9. Adverse events leading to temporary interruption of study treatment

The action taken for an adverse event is stored in SDTM.AE.AEACN. An AE is considered to be an AE leading to discontinuation if AEACN = 'Drug interrupted'.

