5.4.4.3. AE displays

The following types of summary display are used:

- Overview of AEs;
- AEs by primary system organ class (SOC) and preferred term (PT);
- AEs by preferred term (PT);
- AEs by AESI category and PT;
- AEs by maximum intensity and PT.

CONFIDENTIAL – FOIA Exemptions Apply in U.S.

Status: Approved, Date: 20 September 2023

Overview of AE summaries display subjects having any AE, any severe AE, any drug-related AE, any AE leading to study drug discontinuation, any serious AE, any drug-related serious AE, or any fatal serious AE.

AE summaries by grouping term(s) (e.g., SOC, PT, AESI category, maximum intensity) display the number and percentage of subjects having any AE and having an AE in each grouping term. They are sorted by descending frequency of grouping term in the ponesimod 40 mg arm, then the ponesimod 20 mg arm, and finally the ponesimod 10 mg arm. If the frequencies in any grouping term are still the same, alphabetical order is used. Maximum intensity order is fixed as mild, moderate, severe.

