5.4.4.4.3. Treatment-emergent AEs leading to study treatment discontinuation

The following summaries are presented:

- TEAEs leading to study treatment discontinuation by SOC and PT (frequency);
- TEAEs with onset on Day 1 of first ponesimod administration leading to study treatment discontinuation, by SOC and PT (frequency) single table with a column for ponesimod 10 mg only.

A separate listing including all AEs leading to study treatment discontinuation is provided for AP3 on the PAS.

Treatment emergent SAEs with onset of Day 1 of first ponesimod administration leading to study treatment discontinuation, by SOC and PT (frequency) was presented in the Interim Analysis CSR and is not planned to be presented in the Final CSR.

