5.4.4.4.4. Treatment-emergent AEs leading to temporary interruption of study treatment

A listing including all AEs leading to temporary interruption of study treatment is provided for AP3 on the PAS.

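### SAP 5.4.3.9 labels adverse events with action 'Drug interrupted' as leading to discontinuation, contradicting its own heading and 5.4.3.8; probably a copy-paste slip, but it sits in a derivation rule

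*SAP*

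**What the plan says.** SAP 5.4.3.8 and 5.4.3.9 are consecutive definitions based on the recorded action taken (AEACN).

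- 5.4.3.8 covers discontinuation: "An AE is considered to be an AE leading to discontinuation if AEACN = 'Drug withdrawn".
- 5.4.3.9 is headed "Adverse events leading to temporary interruption of study treatment", but its rule says that an AE is "considered to be an AE leading to discontinuation if AEACN = 'Drug interrupted".

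The outputs keep the two categories apart.

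- 5.4.4.3 puts "any AE leading to study drug discontinuation" in the AE overview. Under 5.4.4.3.2 the treatment-emergent overview is produced both as frequencies and per 100 subject-years.
- 5.4.4.4.3 plans "TEAEs leading to study treatment discontinuation by SOC and PT (frequency" and a separate listing of discontinuation AEs.
- 5.4.4.4.4 plans "A listing including all AEs leading to temporary interruption of study treatment".
- 6.10.3 gives Covid-19 infection AEs one row for interruption (iv) and another for discontinuation (v).

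The protocol also separates them. Section 3.6.2 allows study drug to be paused because of an AE. Sections 3.10.2 and 5.6 make AEs leading to premature discontinuation a safety endpoint, summarized by crude incidence.

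**The concern.** Two consecutive derivation rules assign the same label to two different actions, and no sentence assigns the label that the second section is about. AEs leading to discontinuation are a named protocol endpoint and a headline tolerability figure, in a study whose first objective is long-term safety and tolerability. SAP section 1 assigns most of the programming, including these outputs, to a CRO, which works from the rule text.

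If that text is followed, a patient who paused ponesimod for an AE and resumed is reported as having an AE that led to stopping. The treatment disposition tables take discontinuation from treatment-termination records and the study drug log (5.2.1.5), so they would not count that patient as discontinued. Two sections of the report could then disagree.

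**Working it through.** No sample size, power or other figure is involved, so the check is a comparison of texts.

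**1. What the rules say together.** Both say 'if', not 'only if'. Taken literally:

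| Flag | AEACN values that set it | Source |
|---|---|---|
| AE leading to discontinuation | Drug withdrawn, or Drug interrupted | 5.4.3.8 and 5.4.3.9 |
| AE leading to temporary interruption | none stated | no sentence in the SAP |

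SAP 5.4.1.1 does define a treatment interruption from the study drug log. That is an exposure variable and does not link a pause to an AE.

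**2. What the surrounding structure says.**

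| Definition | Heading | Matching output |
|---|---|---|
| 5.4.3.8 | discontinuation | 5.4.4.4.3 table and listing; 5.4.4.3 overview row; 6.10.3 (v) |
| 5.4.3.9 | temporary interruption | 5.4.4.4.4 listing; 6.10.3 (iv) |

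Each definition heading has its own outputs. The criterion in 5.4.3.9 (Drug interrupted) fits its heading; only the label between them does not.

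**3. Is it a declared change?** SAP 6.2 lists changes and clarifications to the protocol-planned analyses. None mentions widening AEs leading to discontinuation to include interruptions.

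**4. Are the affected outputs still planned?** Some Day 1 tables, including the Day 1 discontinuation table in 5.4.4.4.3, are dropped from the Final CSR. The overview row, the main discontinuation table and listing, the interruption listing and the Covid-19 table are retained.

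**5. Direction of the error if followed literally.** Take any one treatment group. Let W be the subjects with at least one withdrawal AE, and I the subjects with at least one interruption AE. The intended count is |W|. The literal count is

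|W ∪ I| = |W| + |I| − |W ∩ I| ≥ |W|.

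The percentage therefore cannot fall, and it rises as soon as one subject has an interruption AE and no withdrawal AE. For the rate per 100 subject-years, the observation time in 5.4.4.2 does not depend on AEACN, so each interruption event added raises the rate.

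**6. Size.** This needs |I| and |W ∩ I|. Neither document reports AEs by action taken, so no figure can be derived.

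**The case against.** The strongest reply is that the SAP resolves its own meaning. The section heading names temporary interruption, the criterion is the matching AEACN value, and the definition headings pair one to one with the output headings. The two separate rows in 6.10.3 show that the authors treat the categories as distinct. To merge them, a programmer would have to ignore the heading, pool two sections, and leave the interruption listing and Covid-19 row (iv) without a derivation. The SAP has other clerical slips of the same kind: 5.2.1.6 takes core-study completion from the extension dataset, and 5.4.3 names the core AE dataset twice where both studies are meant.

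This stands as to intent and likelihood. It does not remove the defect, because the rule sentence is still wrong. A production programmer following the heading and a validation programmer following the sentence would derive different flags.

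The reply also limits the conflict with disposition. Disposition reasons do not come from AEACN, and the extension categories split AE-related stopping across physician decision, subject withdrawal and protocol-specified criteria. Exact agreement with the AE table is not assured even under correct programming. Equally, a surplus of resumed patients in the discontinuation table could be noticed against disposition, so the error need not stay hidden.

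A reader might infer two stronger things. One is that the final discontinuation table will contain the interruptions; the documents show only that the literal text permits it. The other is a numerical inflation of the discontinuation rate; that needs withdrawal and interruption rates which the documents do not supply.

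**Conclusion.** The contradiction is real and lies in an operative rule. As worded, 5.4.3.9 conflicts with its heading, with 5.4.3.8, with the separate outputs in 5.4.4.4.3, 5.4.4.4.4 and 6.10.3, and with the protocol endpoint. It is not a declared change. Followed literally, it would add interruption AEs to the discontinuation outputs and leave the interruption outputs without a rule. The effect on the discontinuation rate would be zero or upward, and its size cannot be estimated from the documents.

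Severity is low. This is very probably a label carried over from 5.4.3.8, and a careful programmer would read it as intended. The conclusion assumes only that the AEACN rules are applied as equality tests, as the SAP writes them.

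**What to change.** In SAP 5.4.3.9, change the label in the rule from leading to discontinuation to leading to temporary interruption of study treatment, and keep the criterion AEACN = 'Drug interrupted'. Section 5.4.3.8 then stands alone, and only 'Drug withdrawn' feeds the overview row, the discontinuation table and listing, and row (v) of the Covid-19 table. The interruption listing and row (iv) gain their derivation rule.

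The cost is one phrase in the SAP, plus a check that any flags already programmed follow the corrected rule. No new data, outputs or changes to trial conduct are needed.
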